## 8.2 Appendix B: Coding Schema

As part of coding procedures, a manual was developed which included definitions of age related concerns categorized within each GA domain, of who initiated the discussion, and the possible response qualities from the oncologist. Five coders each underwent 40 hours of in-person training with sub-investigators and the PI. In addition, all coders read and studied the coding manual. Coders transitioned from training to independent coding only after full consensus was met on all 25% training transcripts as a group.

The GA domains include physical performance, functional status, cognitive, comorbidity, polypharmacy, nutritional status, psychological status, and social support. Explicit discussions related to cognition (e.g., how is your memory?) were captured as well as implicit discussions (e.g., are you remembering to take your medications). Within each GA domain there are numerous age-related concerns, which are listed in the coding manual as subcodes, with the addition of an unspecified subcode for each concern. Developing the coding scheme for who initiated the concern involved identifying who initially brought up the concern during the clinic visit (e.g oncologist, patient, caregiver, other health care provider, friend, family member). For response quality coding, the coders identified whether an age-related concern was specifically asked about or only mentioned, and whether later acknowledged through a follow-up question, reflection, or validation. Then GA concerns were reviewed to detect whether or not they were appropriately addressed by the oncologist or not addressed (e.g. dismissed, ignored, shut down, minimized) at all.

The coding procedures consist of initially reading the transcript to look for the geriatric domains discussed, the identification of any age related concern, and determining who initiated those concerns during the clinic visit. The second reading of the transcript was to identify the response quality of each age related concern and any discussions of GA recommendations to address those concerns.

All coders were paired together rotating coding partners throughout the coding process to ensure groups did not drift in their coding process over time. Each coder coded independently. Then, each week met with his or her paired coder to complete one coding consensus table for each transcript. In addition, each week all five coders met and came to consensus concerning the transcripts designated for inter-rater reliability, creating a final consented coding table. Twenty percent of the transcripts were coded by all five coders to establish inter-rater reliability, with the remaining transcripts dually coded. The final consensus tables will be used to analyse the data.

Because all final codes were discussed and agreed upon by at least two trained coders, reliability and consistency of the codes throughout all observations is very high.

### 8.2.1 COACH Coder Interrater Reliability

To establish interrater reliability between all coders, 20% of all transcripts will be coded by all coders. These transcripts will be allocated over the entire duration of time coding is conducted to test for ongoing agreement among all coders. Transcripts are randomly assigned to each coder. Every 5th transcript is coded by all coders and will be used for IRR. If an overall agreement is not  $\geq 70\%$ , discrepancies will be identified and targeted training will take place. Also to prevent coding drift, the teams of coders will alternate. Review the table below to explain this strategy.

Transcript #	Coder 1	Coder 2	Coder 3	Coder 4	Coder 5
1	X	X			
2		X	X		
3			X	X	
4				X	X
5	X	X	X	X	X

Due to the conditional coding structure of this study, we will report percent agreements for 3 coding areas. These percent agreements will be calculated on the 20% of transcripts that are coded by all coders, since the remainder of transcripts are dual coded. The gold standard for the calculation of percent agreement will be the consensus coding, which will be reached by all coders.

**8.2.2 % Agreement for 3 Coding Areas**

(1) First is the percent of agreement on the **number of geriatric concerns mentioned** in the transcript, without regard to who initiated the conversation. This is calculated on the difference score between the coder and consensus and a percent of those coded correctly is divided by those coded incorrectly. The equation is as follows: consensus # - abs(coder # - consensus #) / consensus #) x 100). An average of all individual coders’ agreements will be reported.

(2) Second is the percent agreement on **the category of geriatric domain discussed**. This will be calculated by each individual coder agreement with the consensus of whether each geriatric domain (a total of 8) was present or absent. An average of all coder agreements will be computed.

(3) Lastly is the percent agreement on **the physician’s concern response quality**. Response quality will be considered for only the same concerns that all coders coded for individually. The agreement will be calculated based on the coder’s agreement with the consensus codes on the three response quality categories: appropriately acknowledged, appropriately addressed, and dismissed. An average of all coder agreements will be computed.

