1.8.5. The research team has experience with the assessment of patient-physician communication (using audio-recordings, surveys, and chart reviews) in the setting of advanced cancer. [name], an expert in patient-centered communication and co-investigator on this study, has conducted multi-method research to study patient-physician interactions using analyses of patient and physician surveys and medical record audits.⁷⁶ His research team has helped to establish that patient-centered communication is associated with improved information exchange, reduced symptom burden, lower health-care costs, and greater patient involvement in decision making.⁷⁷⁻⁷⁹ The measures to assess decision making in [name] NCI-funded RO1 ([name] is a co-investigator) have been adapted for patients with advanced cancer.^{67,68} Using two trained coders, we examined the audio-recorded interactions between the older patients (n=32) with advanced cancer and their oncology physicians (at 8 different sites) to assess number of discussions related to geriatric domains brought up by patient and/or caregiver that were addressed by the oncology physician and the number of "missed opportunities" (i.e., concerns brought up by patients and caregivers that were not adequately addressed by the oncology physician). We found that at baseline, there were 26 discussions and 26 missed opportunities among 32 audio-recorded visits. Fifty percent of visits had 0 age-related discussions; the median was 1 (range 1-3). The majority of missed opportunities were related to functional ability (e.g., not taking medicines correctly), physical functioning (e.g., inability to climb stairs, falls), social support (e.g., difficulty getting to appointments), and medications (e.g., polypharmacy, drug interactions). This study was not elderly specific and did not incorporate GA (which can identify deficits as described above), but the results provide an estimate of the baseline number of discussions about age-related issues that occur in usual care within oncology. We were able to utilize this data to help gather usual care information to inform our analytic plan.

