#### **3.6.3 Coding Schema for Transcripts of Audio Recordings (Appendix B)**

The coding schema includes definitions for each code and the specific steps the coders performed during the coding process. The coding procedures involve an initial reading of the transcript to identify specific geriatric concerns and the initiator of the concerns, followed by a second reading, in which response quality and interventions implemented due to concerns are identified.

Five coders were involved in the coding process, with 20 percent of the transcripts coded by all five coders to establish and maintain inter-rater reliability; the remaining transcripts were all dually coded. For each transcript, whether dually coded or coded by the entire coding team, a consensus was agreed upon and a final coding table created for that transcript. These final consensus tables are what will be utilized in the analysis of the data.

Due to the coding schema involving a conditional coding structure, inter rater reliability involved percent agreement in 3 coding areas: number of geriatric concerns, the category of geriatric domain discussed, and the physician's response quality. For number of geriatric concerns, the percent agreement was calculate using the difference in numbers between each coder and the consensus. An average of all coder agreement was calculated for category of geriatric domain and physician response quality. If inter-rater agreement percentages fell below 70%, the coding team would meet for additional training. The principal investigator remained involved in the coding process and provided guidance or adjudication when necessary. (See Appendix B for a more detailed description of coding).

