**8.2.3 Computation**

We will compute percent agreement scores for the three defined areas. Information will be available in real time to allow for retraining if necessary and ongoing monitoring. All scores will be maintained in a data file and summary reports will be computed at study end (or when required). The table below provides an example of how all three percent agreements will be calculated. The three percent agreements are highlighted in blue.

Note the computation varies because area one is a count variable, and areas two and three are all dichotomous variables (yes/no). For the number of geriatric concerns mentioned, percent agreement is calculated on the difference score between the coder and consensus and a percent of those coded correctly divided by those coded incorrectly.

Percent Agreement	Variable	Coder A	Coder B	Coder B	Consensus	A and Consensus	B and Consensus	C and Consensus	% Agreement
# of Concerns	Number of geriatric concern mentioned	7	5	5	5	0%	100%	100%	67%
Geriatric Domain Mention	Functional Status	1	0	1	1	100%	0%	100%	67%
	Nutritional Status	1	1	1	1	100%	100%	100%	100%
	Cognition	0	0	0	0	100%	100%	100%	100%
	Physical Performance	1	1	1	1	100%	100%	100%	100%
	Comorbidity	0	0	0	0	100%	100%	100%	100%
	Polypharmacy	1	0	1	1	100%	0%	100%	67%
	Social Support	0	1	1	1	0%	100%	100%	67%
	Psychological Status	0	1	0	0	100%	0%	100%	67%
									83%
Response Quality: Acknowledged	Concern 1	1	1	1	1	100%	100%	100%	100%
	Concern 2	0	0	0	0	100%	100%	100%	100%
	Concern 3	1	1	1	1	100%	100%	100%	100%
	Concern 4	1	1	1	0	0%	0%	0%	0%
	Concern 5	0	0	1	1	0%	0%	100%	33%
Response Quality: Addressed	Concern 1	0	0	0	0	100%	100%	100%	100%
	Concern 2	0	0	0	0	100%	100%	100%	100%
	Concern 3	0	1	0	1	0%	100%	0%	33%
	Concern 4	1	1	1	1	100%	100%	100%	100%
	Concern 5	0	0	0	0	100%	100%	100%	100%
Response Quality: Dismissed	Concern 1	0	0	0	0	100%	100%	100%	100%
	Concern 2	0	0	0	0	100%	100%	100%	100%
	Concern 3	0	1	0	1	0%	100%	0%	33%
	Concern 4	1	1	1	1	100%	100%	100%	100%

	Concern 5	0	0	0	0	100%	100%	100%	100%
	Mention of Geriatric Assessment	1	0	1	1	100%	0%	100%	67%
	Assess values/goals for treatment outcome	1	1	1	1	100%	100%	100%	100%
	Elicit caregiver perspective/input	0	0	0	0	100%	100%	100%	100%
	Discussed health care proxy	1	1	1	1	100%	100%	100%	100%
General Interventions	Goals of care preferences	0	0	0	0	100%	100%	100%	100%
	Confirm health care proxy in chart	0	1	0	0	100%	0%	100%	67%

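### The SAP's equation for agreement on the number of concerns contradicts its own worked example (87% against 67%) and has no rule for a consensus count of zero

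*SAP*

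**What the plan says.** SAP Appendix B reports percent agreement against the consensus coding in three areas: number of concerns, geriatric domain, and physician response quality. It uses the 20% of transcripts read by all five coders.

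For the first area, 8.2.2 bases the figure on the difference between coder and consensus, adds that "a percent of those coded correctly is divided by those coded incorrectly", and then gives the rule: "The equation is as follows: consensus # - abs(coder # - consensus #) / consensus #) x 100". Section 8.2.3 repeats the wording ("a percent of those coded correctly divided by those coded incorrectly") and explains that "Note the computation varies because area one is a count variable, and areas two and three are all dichotomous variables (yes/no".

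It then introduces the table: "The table below provides an example of how all three percent agreements will be calculated". The row for this area, with three coders, the consensus, three agreements and the mean, reads "Number of geriatric concern mentioned 7 5 5 5 0% 100% 100% 67" percent.

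The action threshold appears twice. SAP 3.6.3 says: "If inter-rater agreement percentages fell below 70%, the coding team would meet for additional training". SAP 8.2.1 applies 70% to an overall agreement figure that it does not define.

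**The concern.** An equation and an example presented as its application should give the same number. Here they do not, and nothing in the SAP says which governs. An analyst who programs the equation and one who programs the table would report different reliability for the same codes.

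The number of age-related discussions is the response for Secondary Aim 1 (Protocol 15.3; SAP 4.3). Agreement on the number of concerns is the reliability figure closest to that response. A reader could not tell which statistic had been reported, and the 70% check could depend on the choice.

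**Working it through.** **Inputs** (SAP 8.2.3, example row): coder counts 7, 5, 5; consensus 5; printed agreements 0%, 100%, 100%; printed mean 67%.

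**1. Reproducing the printed 67%.** Exact match (100% if coder equals consensus, otherwise 0%) gives 0, 100, 100; mean 200/3 = 66.7%. This returns the printed figure, but the SAP does not state the rule for this area.

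**2. The equation, evident bracketing:** (consensus − |coder − consensus|) / consensus × 100.
- Coder count 7: (5 − 2)/5 = 60%.
- Coder count 5, twice: (5 − 0)/5 = 100%.
- Mean: 260/3 = 86.7%, which is 20 points above the table.

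**3. Whether the unbalanced bracket explains the gap.** It does not.
- 5 − (|coder − 5|/5) × 100 gives −35, 5, 5; mean −8.3.
- (5 − |coder − 5|/5) × 100 gives 460, 500, 500; mean 486.7.

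Neither can be intended, and neither gives 0, 100, 100.

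**4. The verbal rule, correct divided by incorrect.** The coder with 7 scores 5/2 = 250%. The other two have 5/0, which is undefined, so there is no mean. Counted over coders it is 2/1 = 200%. It gives no usable agreement figure.

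**5. Where the equation fails** (illustrative counts):

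| Consensus | Coder | Equation | Exact match |
|---|---|---|---|
| 10 | 12 | 80% | 0% |
| 1 | 2 | 0% | 0% |
| 1 | 3 | −100% | 0% |
| 0 | any | undefined | 100% if coder is 0, otherwise 0% |

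**6. The 70% check on the example.** The domain area averages 83.3% (the table prints 83%). The fifteen response-quality rows average 80.0%, from means of 66.7% for acknowledged, 86.7% for addressed and 86.7% for dismissed.

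| Reading of the 70% rule | Exact match | Equation |
|---|---|---|
| Count area alone | 66.7%: retrain | 86.7%: no action |
| Mean of three areas | (66.7 + 83.3 + 80.0)/3 = 76.7%: no action | (86.7 + 83.3 + 80.0)/3 = 83.3%: no action |

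The choice of rule changes the decision in this example only if 70% is applied per area.

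**The case against.** The strongest reply is that the documents do favour one rule. Protocol 7.2 and SAP 3.6.3, 8.2.2 and 8.2.3 all base count agreement on the difference from consensus, and 8.2.3 says the count is handled differently from the yes/no items. On that view the example row is a slip, scored like the dichotomous rows below it. This stands and decides the form of the fix. It does not remove the contradiction, because the table is offered as the way agreement will be calculated.

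Four stronger readings are tempting, and the documents do not support them.
- **Three rival rules.** The correct-over-incorrect wording leads into the equation and reads as a loose gloss. It is wrong as written but yields no competing figure.
- **The 70% trigger necessarily flips.** The plural in SAP 3.6.3 allows a per-area reading. The overall agreement in 8.2.1 may mean an average, and then the example triggers nothing. The example is also one illustrative transcript with three coders.
- **The equation would be undefined for about half of transcripts.** Protocol 1.8.5 says of the pilot: "Fifty percent of visits had 0 age-related discussions; the median was 1 (range 1-3". That count covers matters raised by patient or caregiver and addressed by the physician, and the same 32 visits held 26 missed opportunities. SAP 8.2.2 counts concerns mentioned, whoever raised them. The pilot was not specific to older patients, whereas trial patients need at least one impairment other than polypharmacy. The quoted sentence is also inconsistent in itself, with half the visits at 0 but a range starting at 1. Zeros are plausible; their share cannot be taken from this source.
- **The PCORI primary result is at risk.** The analysis uses final consensus tables (SAP 3.6.3). Other controls exist: 40 hours of training, full consensus on training transcripts, at least two coders per transcript, rotating pairs, and investigator adjudication.

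**Conclusion.** The equation and the example contradict each other: 86.7% against 66.7% on the same row. This assumes only the evident bracketing, and no literal bracketing rescues the example. The equation is also incomplete, being undefined at consensus 0 and negative when a coder's count exceeds twice the consensus.

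The consequence is limited to the reported reliability of the count and, on a per-area reading of 70%, to the retraining decision. The consensus-based outcome, the model and the treatment test are unaffected. The documents do not say which rule produced any agreement figure already computed. Much of the coding is described in the past tense, so the practical effect may now be mainly on what is reported.

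**What to change.** 1. In SAP 8.2.2, keep the difference-based rule already described in Protocol 7.2 and SAP 3.6.3, and write it as max(0, 1 − |coder − consensus| / consensus) × 100. At consensus 0, score 100% if the coder is also 0 and 0% otherwise.
2. Delete the correct-divided-by-incorrect wording in 8.2.2 and 8.2.3.
3. Correct the example row to 60%, 100%, 100%, mean 87%.
4. State in 3.6.3 and 8.2.1 whether 70% applies to each area or to the average of the three.
5. Recompute the reported agreement from the individual coder scores, which 8.2.3 says are kept in a data file. State which rule was used for any figure already computed.

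Exact-match percentage can be reported alongside. Replacing the rule with exact match or an intraclass correlation is a matter of preference and is not needed here; a 70% agreement threshold would not carry over to an intraclass correlation.

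The cost is SAP wording and a re-run on stored scores, with no new coding. The reported figure may move either way. It cannot fall on transcripts with a nonzero consensus that had been scored by exact match. Bringing in consensus-0 transcripts that had been left out could raise or lower it.

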**8.2.3 Computation**

We will compute percent agreement scores for the three defined areas. Information will be available in real time to allow for retraining if necessary and ongoing monitoring. All scores will be maintained in a data file and summary reports will be computed at study end (or when required). The table below provides an example of how all three percent agreements will be calculated. The three percent agreements are highlighted in blue.

Note the computation varies because area one is a count variable, and areas two and three are all dichotomous variables (yes/no). For the number of geriatric concerns mentioned, percent agreement is calculated on the difference score between the coder and consensus and a percent of those coded correctly divided by those coded incorrectly.

Percent Agreement	Variable	Coder A	Coder B	Coder B	Consensus	A and Consensus	B and Consensus	C and Consensus	% Agreement
# of Concerns	Number of geriatric concern mentioned	7	5	5	5	0%	100%	100%	67%
Geriatric Domain Mention	Functional Status	1	0	1	1	100%	0%	100%	67%
	Nutritional Status	1	1	1	1	100%	100%	100%	100%
	Cognition	0	0	0	0	100%	100%	100%	100%
	Physical Performance	1	1	1	1	100%	100%	100%	100%
	Comorbidity	0	0	0	0	100%	100%	100%	100%
	Polypharmacy	1	0	1	1	100%	0%	100%	67%
	Social Support	0	1	1	1	0%	100%	100%	67%
	Psychological Status	0	1	0	0	100%	0%	100%	67%
									83%
Response Quality: Acknowledged	Concern 1	1	1	1	1	100%	100%	100%	100%
	Concern 2	0	0	0	0	100%	100%	100%	100%
	Concern 3	1	1	1	1	100%	100%	100%	100%
	Concern 4	1	1	1	0	0%	0%	0%	0%
	Concern 5	0	0	1	1	0%	0%	100%	33%
Response Quality: Addressed	Concern 1	0	0	0	0	100%	100%	100%	100%
	Concern 2	0	0	0	0	100%	100%	100%	100%
	Concern 3	0	1	0	1	0%	100%	0%	33%
	Concern 4	1	1	1	1	100%	100%	100%	100%
	Concern 5	0	0	0	0	100%	100%	100%	100%
Response Quality: Dismissed	Concern 1	0	0	0	0	100%	100%	100%	100%
	Concern 2	0	0	0	0	100%	100%	100%	100%
	Concern 3	0	1	0	1	0%	100%	0%	33%
	Concern 4	1	1	1	1	100%	100%	100%	100%

	Concern 5	0	0	0	0	100%	100%	100%	100%
	Mention of Geriatric Assessment	1	0	1	1	100%	0%	100%	67%
	Assess values/goals for treatment outcome	1	1	1	1	100%	100%	100%	100%
	Elicit caregiver perspective/input	0	0	0	0	100%	100%	100%	100%
	Discussed health care proxy	1	1	1	1	100%	100%	100%	100%
General Interventions	Goals of care preferences	0	0	0	0	100%	100%	100%	100%
	Confirm health care proxy in chart	0	1	0	0	100%	0%	100%	67%
	List emergency contacts in chart	0	0	1	0	100%	100%	0%	67%
	Confirm Advanced Directives in chart	0	0	0	0	100%	100%	100%	100%
	Discuss advanced directive	1	1	1	1	100%	100%	100%	100%
	Change chemo regimen	0	0	1	1	0%	0%	100%	33%

[figure not shown]
**8.3 Appendix C: Data that will inform Consort Diagram**

COACH	Total S# Patients (Excludes Registration Errors) (Visit 0)	Enrolled (Excludes Registration Errors)	Total # Patients With Baseline Packets Received (Visit 1)	Total # Patients With 4-6 Week Packets Received (Visit 2)	Total # Patients With 3 Month Packets Received (Visit 3)	Total # Patients With 6 Month Packets Received (Visit 4)	Total Active with Missing Data (missing Forms)	Total Currently Active (excludes withdrawn and deceased)	Total Withdrawn	Total Deceased During Study	Total Deceased Post Study
Patient											
Caregiver											
Totals											

COACH	Total # Screen Registered (Includes Registration Errors)	# Screen Failures (ineligible, deceased)	# Screen withdrawals	# Pending Enrollment (Screen Registered but not Enrolled)	# Registration Errors	# Enrolled
Patient						

# Patients Withdrawn (w/d) or Expired during given assessment period					
Time period	Screen	Baseline	4-6 Weeks	3 month visit	6 month visit
Withdrawn					
Expired					

8.4 Appendix D: COACH Study Cluster Randomized CONSORT Flow Diagram

1-sites are no longer associated with their respective NCORP or with the URCC Research Base; 2-clusters that maintained IRB approval but never actually enrolled any participants

3-discussions about age-related issues during clinic consultation-assessed using audios of baseline visit with physician

4-satisfaction with communication regarding age-related issues-assessed using HCCQ's collected at baseline.

5-irretrievable, site miscommunication, technical difficulty, or protocol violation
